7.3 Lost to Follow-up

A patient will be considered lost to follow-up if he or she repeatedly fails to return for scheduled visits and is unable to be contacted by the study site staff.

The following actions must be taken if a patient fails to return to the clinic for a required study visit:

- The site will attempt to contact the patient and reschedule the missed visit as soon as possible; counsel the patient on the importance of maintaining the assigned visit schedule; and ascertain if the patient wishes to and/or should continue in the study.
- Before a patient is deemed lost to follow-up, the Investigator or designee will make every effort to regain contact with the patient (where possible, 3 telephone calls and, if necessary, a certified letter to the patient's last known mailing address or local equivalent methods. These contact attempts should be documented in the patient's medical record or study file.
- Should the patient continue to be unreachable, he or she will be considered to have withdrawn from the study with a primary reason of lost to follow-up.

8 STUDY ASSESSMENTS AND PROCEDURES

Planned timepoints for all assessments are provided in the Schedule of Activities (Section 1.3).

8.1 Study Periods

The study will comprise 3 phases:

1. **Pre-Treatment Phase** (up to 5 weeks), in which all patients will be assessed for eligibility. The pre-treatment phase will consist of initial screening assessments (Visit 1) and a Run-in period (Visit 2 through Visit 3).
2. A **Treatment Phase** (4 weeks), in which all patients will return to the clinical for randomization and start of treatment (Visit 3 – Day 1) followed by weekly visits (Visit 4 – Day 8 [\pm 1 day], Visit 5 – Day 15 [\pm 1 day], Visit 6 – Day 22 [\pm 1 day]) until Visit 7 – Day 29 (\pm 1 day), and
3. A **Follow-up Phase** (2 weeks), in which patients who complete Visit 7, will be asked to return for an End-of-Study Follow-up visit (Visit 8 – Day 43 [\pm 3 days]) for assessment of treatment outcome (e.g., safety, durability of effect).

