
Study Design:
	
A phase 2a, randomized, double-blind, PBO-controlled, multicenter trial to provide proof-of-principle efficacy of BOS-589 in IBS-D patients and to inform dose selection for subsequent development.
 
The study will comprise 3 phases:
 
A Pre-treatment Phase of up to 5 weeks, in which all patients will be assessed to determine eligibility. This phase will consist of initial screening assessments after which eligible patients will enter a Run-in Period of up to 3 weeks.
 
During the Run-in period the patients will complete an electronic diary to collect daily information related to their IBS-D symptoms, bowel function, and rescue medication use,
	

[figure not shown]
	
to confirm disease activity, and diary compliance.
 
Upon completion of the Run-in Period, patients will return to the study site to confirm eligibility for randomization into the double-blinded Treatment Phase.
 
A Treatment Phase, in which eligible patients will be randomized (1:1:1) to receive BOS-589 or PBO twice daily (bid) for a total of 4 weeks. BOS-589 will be administered at 1 of 2 dose levels. Patients will be randomized to the following cohorts:
 
 • Cohort 1 (High Dose): 200 mg BOS-589 bid orally; • Cohort 2 (Low Dose): 50 mg BOS-589 bid orally; • Cohort 3 (PBO): matching PBO oral tablets bid. 
During the treatment phase, patients will continue to complete the electronic diary to collect daily information related to their IBS-D symptoms, bowel function, and rescue medicine.
 
A Post-treatment Phase, in which all patients who complete 4 weeks of treatment will return to the clinical for a 2-week follow-up visit.
 
Patients who discontinue treatment early will be asked to return to the clinic for safety assessments.

Study Population:	Male and female patients 18 to 65 years of age, inclusive, with a diagnosis of IBS-D.
Number of Patients Planned:	Approximately 300 patients will be screened with the intent of randomizing 132 patients for the study.
Duration of Patient Participation and Study:	
The duration of patient participation is anticipated to be up to 11 weeks.
 
The duration of the study is anticipated to be approximately 12 months.

Study Sites:	Up to 66 sites in the United States.
Investigational Product:	BOS-589 (oral doses bid).
Reference	Matching PBO (oral doses bid).

Treatment:	
Concomitant Product:	Not applicable.

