^b Procedures performed at Visit 7/End of Treatment or upon Early Termination. Early Termination procedures are to be performed in close proximity to discontinuation of dosing for patients who are withdrawn from the study. Other procedures may be performed at Investigator or Sponsor discretion.
^c Full physical exam to be conducted at Screening. Symptom-directed physical examinations should be conducted at subsequent visits.
^d Height and body mass index to be collected at Screening Visit only.
^e Hematologic, complete serum chemistry, urinalysis panels and fecal calprotectin to be completed as noted in [Appendix 1](#). Patients should refrain from food or drinks (other than water) for at least 8 hours prior to obtaining a fasting glucose level.
^f Pharmacokinetic (PK) serial blood samples are to be collected on Day 1 and Day 15 at predose and at 0.5, 1, 2, and 4 hours postdose. If PK serial blood samples cannot be collected on Day 15, PK serial blood samples should be collected on Day 22. A predose sample will be obtained on all other Treatment Study Visits. Allowable sampling windows for PK blood draws will be 30 minutes prior to dosing for the predose sample, then ± 5 minutes for 0.5 and 1 hour postdose, and ± 10 minutes for 2 and 4 hours postdose.
^g Data will be collected daily for entire Run-in Period.
^h Data will be collected daily until Early Termination or until End-of-Study Visit, whichever is later.

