4 STUDY DESIGN

4.1 Overall Design

This study is a phase 2a, randomized, double-blind, PBO-controlled, multicenter trial designed to provide the first proof-of-principle efficacy of BOS-589 in IBS-D patients, and to inform dose selection for subsequent development. The study will consist of a pre-treatment phase, a 4-week double-blind treatment phase, and a 2-week post-treatment follow-up period.

Pre-Treatment Phase: During the pre-treatment phase, patients will be evaluated for up to 5 weeks to assess eligibility. The pre-treatment phase will consist of initial screening assessments and a Run-in period.

After the initial screening assessments have been performed, eligible patients will enter a Run-in period of up to 3-weeks. During the Run-in period, the patients will complete an electronic diary to collect daily information related to their IBS-D symptoms, bowel function, and rescue medicine use, to confirm disease activity and diary compliance. Patients will also be requested to discontinue any prohibited medications during this phase of the study.

Upon completion of the Run-in period, patients will return to the study site to confirm eligibility for randomization into a 4-week double-blinded Treatment Phase.

Treatment Phase: Eligible patients will be randomized (1:1:1) into the following cohorts:

- Cohort 1 (High Dose): 200 mg BOS-589 bid orally
- Cohort 2 (Low Dose): 50 mg BOS-589 bid orally
- Cohort 3 (PBO): matching PBO oral tablets bid orally

During the 4 weeks of double-blind treatment, patients will continue to record their daily IBS-D symptoms, bowel function, and rescue medicine use in the electronic diary, as described in [Section 8.3](#).

Post-treatment Phase: A 2-week post-treatment follow-up visit will occur for patients who complete the Treatment Phase. During the 2 weeks of follow-up, patients should continue to record their daily IBS-D symptoms, bowel function, and rescue medicine use in the electronic diary.

Patients who prematurely discontinue treatment should return to the study center to complete the early termination assessments as soon as possible after stopping the treatment.

Data analyses will occur after all patients in the trial have completed the last visit or procedure shown in the Schedule of Activities, [Section 1.3](#).

Post-study Access to Therapy: No post-treatment access to therapy will be provided to patients randomized in the study.

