7 DISCONTINUATION / WITHDRAWAL

7.1 Discontinuation of Investigational Product

A patient may discontinue from study treatment at any time at his or her own request or may be withdrawn at any time at the discretion of the Investigator for safety, behavioral, or administrative reasons. Discontinuation from the investigational product does not mean discontinuation from the study, and remaining study procedures should be completed as indicated by the study protocol. If a clinically significant finding is identified (including, but not limited to, changes from baseline) after enrollment, the Investigator or qualified designee will determine if any change in patient management is needed. Any new clinically relevant finding will be reported as an AE.

Upon investigational product discontinuation, patients should complete all procedures collected in the Day 29/End-of-Treatment visit as applicable per the Schedule of Activities ([Section 1.3](#)).

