9.2 Sample Size Determination

This is a phase 2a study in which a hierarchical hypothesis test will be employed for the primary efficacy endpoint. The primary endpoint is defined as a change in the 24-hour WAP score at Day 29 compared to baseline (averaged over the week prior to each respective timepoint). Mean change from baseline will be measured as a continuous variable and compared between treatment groups in a hierarchical testing order using a t-test of equal variances and a two-tailed alpha of 0.05.

The sample size was based on the first hypothesis test in the hierarchical plan, with 80% power, two-sided alpha of 0.05, and a standard deviation (SD) of 3 points on the NRS to detect a 1.6 minimum change between treatment groups (N = 120 patients). To account for attrition and a potential higher PBO rate, a total of 132 patients will be randomized to one of 3 treatment groups in a 1:1:1 ratio (44 patients per treatment group).

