9.4.1 Efficacy Analyses

9.4.1.1 Primary Endpoint

This is a proof-of-principle study in which a hierarchical hypothesis test will be employed for the primary efficacy endpoint, defined as a change in the 24-hour WAP score at Day 29 compared to baseline (averaged over the week prior to each respective timepoint). Mean change from baseline will be measured as a continuous variable and compared between treatment groups in the following testing order using a t-test of equal variances and a two-tailed alpha of 0.05:

Hypothesis 1:

Active Treatment Group (Cohort 1 + Cohort 2) versus PBO (Cohort 3);

If statistically significant at $P < 0.05$, then proceed to Hypothesis 2.

Hypothesis 2:

Cohort 1 (High Dose) versus Cohort 3 (PBO);

If statistically significant at $P < 0.05$, then proceed to Hypothesis 3.

Hypothesis 3:

Cohort 2 (Low Dose) versus Cohort 3 (PBO);

If statistically significant at $P < 0.05$ then, proceed to Hypothesis 4.

Hypothesis 4:

Cohort 1 (High Dose) versus Cohort 2 (Low Dose).

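### Protocol passages conflict on what is collected after a patient stops study drug, and the SAP does not say how such patients enter the Day 29 primary analysis

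*Protocol*

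**What the plan says.** **Protocol v3.0, passages that keep the patient in the study**
- 7.1: stopping the drug "does not mean discontinuation from the study, and remaining study procedures should be completed as indicated by the study protocol".
- 6.5: a patient stopped permanently after a dose reduction is followed to the end of the study.

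**Protocol v3.0, passages that can be read as ending participation early**
- Synopsis (1.1): "Patients who discontinue treatment early will be asked to return to the clinic for safety assessments". It mentions no diary or efficacy assessment for these patients.
- 4.1: anyone who stops treatment early comes in for early-termination assessments, while "A 2-week post-treatment follow-up visit will occur for patients who complete the Treatment Phase".
- 7.1, second paragraph: the Day 29/End-of-Treatment procedures are done when the drug is stopped.
- Schedule of Activities (1.3), note b: early-termination procedures are for patients withdrawn from the study, a narrower group than in 4.1.
- Schedule of Activities, note h: "Data will be collected daily until Early Termination or until End-of-Study Visit, whichever is later". If no End-of-Study visit follows, the diary ends at Early Termination.
- 8.1: follow-up is a phase "in which patients who complete Visit 7, will be asked to return". This concerns the Day 43 visit.

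**SAP v1.2**
- Section 7: the Day 29 score is the mean of available diary scores from the 7 days before the Day 29 visit. Visits more than 14 days from calculated Day 29 are excluded. Nothing is imputed.
- Section 5.7: nominal visits drive the analysis. The protocol schedule gives Day 29/End of Treatment and Early Termination a single Visit 7 column.
- Section 9: Day 29 includes early termination, stated for safety analyses only.
- Section 6.1: the ITT set is all randomized patients.
- Section 4: data up to study withdrawal are used however long treatment lasted.

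**The concern.** The primary test compares mean change in worst abdominal pain at Day 29. A patient contributes only with a Day 29 visit score, and that score depends on diary entries and a visit whose collection after stopping drug is described inconsistently. With up to 66 sites, some could keep the diary running under 7.1 while others close the patient out under 4.1 and the synopsis, each in good faith.

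Stopping may be related both to treatment and to outcome. Protocol 7.2 suspends drug for, among other things, four days without a bowel movement or evidence of severe constipation, and 2.2.3 describes a drug that inhibits induced increases in colonic motility. More stopping on active is plausible, though the documents give no rates. If stoppers lack a score, or contribute one from an earlier week, the comparison is no longer the all-randomized comparison at four weeks that the ITT label suggests.

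The SAP does not close the gap. Protocol 9.4.1.4 leaves missing-data methods to the SAP. SAP 5.10 refers to efficacy imputations in Section 7, which contains none. The sensitivity analysis named for the primary endpoint (screening fecal calprotectin under 50 mcg/g) is a subgroup analysis and does not address missing data.

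**Working it through.** **1. The plan's own figure.** Inputs from Protocol 9.2 and 9.4.1.1: difference 1.6, SD 3, two-sided alpha 0.05, pooled active against placebo (2:1), 120 evaluable, 132 randomized.
- Noncentrality = 1.6 / (3 × √(1/80 + 1/40)) = 1.6 / 0.581 = 2.75. Power is 78.0% (noncentral t) or 78.6% (normal approximation), in line with the approximately 80% in SAP 3.4.
- With all 132 (88:44), power is 81.8% (noncentral t).
- Implied allowance for loss = 12/132 = 9.1%. No attrition rate is stated, and the same margin must cover a possibly higher placebo response.

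**2. What the Day 29 rule does with an early stopper.** The window is 29 − 14 = Day 15 to 29 + 14 = Day 43.

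| Situation | Effect on the primary score |
|---|---|
| Diary kept and a true Day 29 visit (7.1, 6.5) | Week before Day 29 is used, off drug |
| Early termination filed as Visit 7, before Day 15 | Excluded by the window |
| Early termination filed as Visit 7, on Day 15 | Days 8 to 14 are scored as Day 29 |
| Early termination not treated as Day 29 for efficacy, and no later visit | No score; dropped from the t-test |

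The documents do not determine which row applies.

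**3. Bias from dropping stoppers.** Assume stoppers improve g points less than those who stay, with the same g in both arms. Each arm's all-patient mean improvement is then the stayers' mean minus m × g, where m is the arm's missing fraction. So:

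available-case difference − all-patient difference = g × (m_active − m_placebo)

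A positive value overstates the benefit of active. The documents give neither g nor m; all values below are assumptions.

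| g | Missing, active vs placebo | Bias (points) | Share of 1.6 |
|---|---|---|---|
| 2 | equal | 0 | 0% |
| 2 | 12% vs 5% | 2 × 0.07 = +0.14 | 9% |
| 2 | 20% vs 8% | 2 × 0.12 = +0.24 | 15% |
| 1.6 | 25% vs 5% | 1.6 × 0.20 = +0.32 | 20% |
| 2 | 5% vs 12% | −0.14 | −9% |
| 2 | 8% vs 20% | −0.24 | −15% |

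If the gap differs between arms, equal loss no longer guarantees zero bias. The error from scoring an earlier week as Day 29 is separate and cannot be sized from the documents.

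**4. Does keeping stoppers gain power?** Suppose 9.1% of active patients stop and lose all drug effect (assumption). The difference becomes 1.6 × (1 − 0.091) = 1.45, and power at 88:44 is 74%. With 5% stopping it is 1.52 and 78%. Neither exceeds the 78.0% at 120, so the case rests on bias and definition.

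**The case against.** The strongest reply is that the protocol's intention is already clear. Section 7.1 separates stopping drug from leaving the study, 6.5 agrees, 8.3 asks for daily entries through the four-week treatment phase, and SAP Section 4 would use the data. No passage says the diary stops when drug stops. The synopsis and 4.1 add a visit; they do not end the diary. Note b can be squared with 7.1 if early termination means study withdrawal, and note h takes the later of two dates. Section 8.1 governs Day 43 only, and completing Visit 7 could include an early-termination Visit 7.

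Much of this stands, and it rules out several stronger readings. A reader might infer that the Day 22 to 28 diary is never obtained from early stoppers. That fixed window belongs to the superseded SAP v1.0 and v1.1, and non-collection follows from only some readings of the protocol. A reader might also infer that the ITT test becomes an analysis of completers. Under SAP v1.2 a patient stopping from about Day 15 may be included, with an earlier week's diary. Nor can 82% against 78% power be presented as a gain from the fix, because it ignores dilution by off-drug patients.

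The reply does not remove the conflict. Note b restricts early termination to study withdrawals while 4.1 applies it to everyone who stops. Note h ends the diary at Early Termination when no End-of-Study visit follows, and 4.1 provides that visit only for completers. The efficacy status of an early-termination visit is not stated anywhere.

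**Conclusion.** The concern holds as an inconsistency with consequences for the primary endpoint. The primary ITT test is an available-case analysis in which the handling of early stoppers is undefined: they may be dropped, notably with a visit before Day 15, or have an earlier week counted as Day 29.

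The possible bias from dropping is modest: 0.14 to 0.24 points (9% to 15% of 1.6) under an assumed 2-point gap and 7 to 12 percentage points more loss on active, zero under equal loss with a common gap, and reversed in sign if placebo loses more. These figures illustrate scale and do not predict it. The textual finding does not depend on them. It warrants correction because sites following the stated rules could lose or mislabel primary-endpoint data.

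**What to change.** **Protocol.** Reconcile 1.1, 4.1, 8.1 and schedule notes b and h with 7.1, so that patients who stop drug without withdrawing consent continue the daily diary and have the Day 29 efficacy assessment at Day 29. Clarify in 7.1 and the schedule that the early-termination visit is recorded separately from Day 29.

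**SAP Section 7.** State that an early-termination visit does not count as Day 29 for efficacy and that off-treatment diary data are used, consistent with SAP Section 4. Pre-specify one missing-data sensitivity analysis for the primary endpoint, and correct the cross-reference in 5.10.

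**Cost.** A wording amendment, which under Protocol 10.1.1 needs approval before a design change is implemented, and an SAP revision. The diary and assessments already exist; for early stoppers they extend beyond what the synopsis and 4.1 describe. Including off-drug data estimates the effect of assignment regardless of adherence and may dilute it, so the SAP should state this choice openly. The rules for stopping treatment are not changed.

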8.2 Screening Assessments

After signing the ICF(s), the patient will undergo the initial screening assessments and procedures as described in the Schedule of Activities (Section 1.3) to determine eligibility.

Eligible patients will enter the Run-in period. At the beginning of the Run-in period, patients will receive instructions for completing an electronic diary to collect daily information related to their IBS-D symptoms, their bowel function, and rescue medication use.

Patients who meet the following requirements will be eligible for participation and immediate randomization into the double-blind treatment phase (i.e., all diary conditions listed must be met to qualify for randomization):

- have completed the daily electronic diary on at least 6 of the 7 days during the week prior to randomization AND at least 11 of the 14 days during the 2 weeks prior to randomization
- over the final 7 days of the run-in period, the patient has an average of WAP scores in the prior 24 hours of 3.0 to 8.0 (on a 0 to 10 numerical rating scale, where 0 indicates no pain and 10 indicates worst pain imaginable),

- over the final 7 days of the run-in period, the patient has an average daily BSFS score ≥ 5.0 (on a 1 to 7 scale, where 1 = hard, lumpy stools, and 7 = watery, liquid stools), and there must be at least 2 days with stool consistency of Type ≥ 6 , and
- have not used any loperamide rescue medication in the 2 weeks prior to randomization

Eligible patients will be instructed to return to the study site for the Baseline visit on Day 1.

If patients do not meet all of the 4 diary conditions required for entry during the 2 week run-in period, the run-in may be extended for an additional week in accordance with investigator judgment (for a total run-in period of up to 3 weeks). Eligibility will then be based on the most recent 14 days of the extended run-in period.

8.3 Efficacy Assessments

The efficacy objectives of the study are to evaluate the effect of BOS-589, relative to PBO after 4 weeks of therapy, on pain, defecation, and key IBS-D related signs and symptoms.

During the 4 weeks of the double-blind treatment phase, patients will be required to access their electronic diary every day, preferably at the same time each day, to record IBS-D symptom data and information related to their bowel function and rescue medication use.

8.3.1 Worst Abdominal Pain

Throughout the 4 weeks of the double-blind treatment phase, patients will be asked to rate their WAP in the past 24 hours. The patient-reported WAP in the past 24 hours will be recorded on a 0 to 10 scale, where 0 corresponds to no pain and 10 corresponds to worst imaginable pain.

8.3.2 Bristol Stool Form Scale

Patients will be asked to record daily stool consistency according to the BSFS most representative of the past 24 hours and worst stool consistency (defined as the loosest stool with the highest BSFS score) in the past 24 hours. The patient-reported BSFS consistency score is based on a 1 to 7 scale where 1 corresponds to a hard stool and 7 corresponds to watery diarrhea (CCI [REDACTED]). Please refer to [Appendix 3](#).

8.3.3 IBS-D Global Symptom Score

Patients will be asked to record daily their overall IBS-D global symptoms in the prior 24 hours. The patient-reported daily IBS-GS is based on a 0 to 4 scale where:

- 0 corresponds to no symptoms;
- 1 corresponds to mild symptoms;
- 2 corresponds to moderate symptoms;
- 3 corresponds to severe symptoms; and
- 4 corresponds to very severe symptoms.

